12.1.3 Statistical Method and Analysis

This section describes the statistical method and analysis per subject basis unless otherwise specified. If more than one lesion is measured for a subject, the data analysis may be performed and presented on a per lesion basis, as appropriate.

The following criteria will be used to define the variables per subject level for subject with multiple lesions:

- Treatment decision is defined as “changed” if there is at least one decision change based on FFR for multiple lesions; if none of the decisions has been changed for the multiple lesions, the treatment decision is defined as “unchanged”.
- For all the continuous variables of FFR, resting indices, CFR, contrast FFR, and RRR, we will use the lowest value in all lesions as the value for that variable in each subject. For the continuous variable of IMR, we will use the highest value in all lesions as the value for IMR in each subject.

The following cutoff values will be used to categorize a continuous variable into a binary variable:

- FFR group is defined as “low FFR” if it is equal to or below 0.8 (the cutoff value of 0.8 is selected in line with contemporary guidelines and previous findings¹¹). However, since this is an observational study, there are no mandated cutoff values for this. Therefore, we will also use cutoff value of 0.75¹² in the analysis.
- Resting indices group is defined as “low resting indices” if it is equal to or below 0.86 (the cutoff value of 0.86 is selected based on previous findings that a baseline Pd/Pa \leq 0.86 is associated with a positive predictive value of 100% for FFR measurement¹³). We will also use the cutoff value of 0.92¹⁴ in the analysis.

Clinical Investigational Plan

- CFR is defined as “low CRF” if it is below 2.0 (the cutoff value of 2.0 is selected based on previous findings^{15,16}).
- IMR is defined as “high IMR” if it is equal to or above 25 (the cutoff value of 25 is selected based on previous findings¹⁷).
- Contrast FFR is defined as “low Contrast FFR” if it is equal to or below 0.83 (the cutoff value of 0.83 is selected based on previous findings¹⁸).
- RRR is defined as “low RRR” if it is smaller than 2.0 (the cutoff value of 2.0 is selected based on previous findings¹⁹).

The following statistical analysis will be performed for each of the study objectives:

1. Characterize the frequency of change in treatment plan when FFR is used compared to the initial decision based on angiography alone

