Frequency and percentage of change in treatment decisions when FFR is used compared to the initial decision based on angiography alone will be presented both per subject level and per lesion level.

2. Characterize the 12-month clinical outcomes (MACE) in subjects in whom the use of FFR did not lead to a change in treatment decision vs. subjects in whom the use of FFR led to a change in treatment decision.

12-month MACE event rate will be summarized using frequency and percentage. Fisher Exact test will be performed to evaluate the association between 12-month MACE event and prospective treatment decisions, i.e. change or no change, based on FFR measurements. A repeated measures logistic regression with generalized estimating equations (GEE) per lesion level will be performed if needed.

3. Characterize the 12 month clinical outcomes (MACE) by FFR values and resting indices respectively.

Fisher Exact test will be performed to evaluate the association between 12-month MACE event and binary FFR and binary resting indices variables respectively using the following FFR and resting indices groups:

- 1) Low FFR group ($FFR \leq 0.8$) and high FFR group ($FFR > 0.8$).
- 2) Low FFR group ($FFR < 0.75$) and high FFR group ($FFR \geq 0.75$).
- 3) Low resting indices group ($Pd/Pa \leq 0.86$) and high resting indices group ($Pd/Pa > 0.86$).
- 4) Low resting indices group ($Pd/Pa \leq 0.92$) and high resting indices group ($Pd/Pa > 0.92$).

A repeated measures logistic regression with generalized estimating equations (GEE) per lesion level will be performed if needed.

A logistic regression will be performed to evaluate the association between 12-month MACE event and continuous FFR and continuous resting indices respectively. A repeated measures logistic regression with generalized estimating equations (GEE) per lesion will be performed if needed.

4. Compare resting indices with FFR values.

Kappa coefficient will be used for binary variables, and correlation will be used for continuous variables to examine agreement between FFR values and resting indices.

5. Characterize the 12 month clinical outcomes (MACE) by other PressureWire-derived indices (CFR, IMR, contrast FFR, RRR).

Clinical Investigational Plan

Fisher Exact test will be used for binary variables, and logistic regression will be used for continuous variables to evaluate the association between 12-month MACE event and other PressureWire-derived indices (CFR, IMR, contrast FFR, RRR) respectively.

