6. Compare other PressureWire-derived indices (CFR, IMR, contrast FFR, RRR) with FFR values

Kappa coefficient will be used for binary variables, and correlation test will be used for continuous variables to examine agreement between FFR values and other PressureWire-derived indices (CFR, IMR, contrast FFR, RRR) respectively.

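### Objectives 4 and 6 use correlation to examine agreement with FFR, which it cannot measure; kappa at Pd/Pa 0.86 and the agreement label for CFR, IMR and RRR also need re-specifying

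*Combined protocol and SAP*

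**What the plan says.** Sections 1.0 and 3.3 word objectives 4 and 6 simply as comparisons with FFR. The methods in section 12.1.3 are more specific. For objective 4, kappa serves the binary forms, while "correlation will be used for continuous variables to examine agreement between FFR values and resting indices". For objective 6, kappa again serves the binary forms; in addition, "correlation test will be used for continuous variables to examine agreement between FFR values and other PressureWire-derived indices (CFR, IMR, contrast FFR, RRR) respectively".

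The binary variables come from the cut-offs in the same section:

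- FFR: 0.80, with 0.75 as a second cut-off.
- Resting indices (Pd/Pa): 0.86, with 0.92 as a second cut-off. The value 0.86 was selected because a Pd/Pa at or below it "is associated with a positive predictive value of 100% for FFR measurement".
- Contrast FFR: 0.83.
- CFR and RRR: below 2.0.
- IMR: 25 or above.

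The section does not say which FFR cut-off is paired with which index cut-off, or which correlation coefficient is meant. Section 12 plans no mean difference, limits of agreement, sensitivity, specificity or predictive values. Section 12.1.2 has every analysis run for all subjects, ACS subjects and stable subjects. For subjects with several lesions, section 12.1.3 takes the lowest value of each variable (highest for IMR), and per-lesion analysis is optional.

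**The concern.** Agreement is the plan's own word for what objectives 4 and 6 examine, and for continuous values the only tool named is correlation. A high r does not show that an index reads close to FFR, and a difference in r between ACS and stable subjects need not mean that the index behaves differently in the two groups.

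Two narrower problems concern kappa. A cut-off picked so that every positive is a true positive may leave FFR-positive lesions undetected, and kappa merges those misses with false alarms into one figure. For CFR, IMR and RRR, which have other scales and in the case of IMR the opposite abnormal direction, calling any statistic a measure of agreement invites a reading that it cannot carry.

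At stake is the interpretation of two of the six objectives: what a reader may conclude about using an alternate index alongside FFR.

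**Working it through.** The plan gives no kappa, correlation, prevalence or sensitivity for these objectives, so there is no figure to reproduce. The cut-offs and the 100% positive predictive value (PPV) come from section 12.1.3. All other inputs are assumptions.

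**1. Correlation and offset.** Let index = FFR + d + error, with assumed FFR SD 0.10 and error SD 0.04.

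- r = 0.10/√(0.10² + 0.04²) = 0.10/√0.0116 = 0.93. The offset d does not appear.
- Concordance correlation = 2(0.10²)/(0.10² + 0.0116 + d²) = 0.02/(0.0216 + d²).
- Limits of agreement = d ± 1.96 × 0.04 = d ± 0.078.

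| Offset d | r | Concordance correlation | Limits of agreement |
|---|---|---|---|
| 0 | 0.93 | 0.93 | -0.08 to 0.08 |
| 0.05 | 0.93 | 0.83 | -0.03 to 0.13 |
| 0.10 | 0.93 | 0.63 | 0.02 to 0.18 |

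Compressing the index to half its scale, with assumed mean FFR 0.81, also leaves r at 0.93, while the concordance correlation falls to 0.46.

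**2. Correlation and spread.** Keep the error SD at 0.04 and vary the FFR SD s: r = s/√(s² + 0.04²). For s = 0.05, 0.08, 0.10 and 0.15, r = 0.78, 0.89, 0.93 and 0.97. The measurement error is the same throughout.

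**3. Kappa and offset.** Suppose contrast FFR = FFR + 0.03 exactly. Then contrast FFR ≤ 0.83 if and only if FFR ≤ 0.80, so no lesion is misclassified and kappa is 1. At this pair of cut-offs the binary analysis absorbs that offset.

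**4. Kappa at Pd/Pa 0.86.** Let p be the share of lesions with low FFR and q the share with Pd/Pa ≤ 0.86. With PPV 100% there are no false positives. Observed agreement is 1 - (p - q), chance agreement is pq + (1 - p)(1 - q), and kappa = 2q(1 - p)/(p + q - 2pq).

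| p | q = 0.10 | q = 0.25 |
|---|---|---|
| 0.30 | 0.14/0.34 = 0.41 | 0.35/0.40 = 0.875 |
| 0.40 | 0.12/0.42 = 0.29 | 0.30/0.45 = 0.67 |
| 0.50 | 0.10/0.50 = 0.20 | 0.25/0.50 = 0.50 |

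In every cell PPV is 100%. Kappa falls short of 1 only through missed lesions, and the kappa value alone does not show that.

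**5. The cut-off pair matters.** In a bivariate normal model (assumed FFR mean 0.78-0.84, SD 0.10; Pd/Pa mean 0.92, SD 0.06; r 0.7-0.9), kappa against FFR 0.80 is 0.21-0.50 at Pd/Pa 0.86 and 0.45-0.71 at 0.92. The 0.92 cut-off gives the higher kappa in all nine scenarios. Against FFR 0.75 the order is mixed. At r = 0.8, Pd/Pa 0.86 and 0.92 give 0.54 and 0.34 with FFR mean 0.84, but 0.40 and 0.55 with FFR mean 0.78.

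**6. Scale.** CFR and RRR are cut at 2.0 and IMR at 25, against 0.80 for FFR, and IMR is abnormal when high. A numerical difference from FFR has no meaning for these three.

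**7. Pairing.** The lowest value is taken separately for each index. In a simulation of subjects with two lesions (assumed FFR mean 0.84, other inputs as in step 5 with r = 0.8, between-lesion correlation 0 to 0.6), the lowest FFR and the lowest Pd/Pa came from different lesions in about 20-28% of subjects.

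**The case against.** The objectives are descriptive, in a registry with no formal sample size calculation. No kappa threshold is set and the plan labels no index as poor, so the risk lies in how results are read. Nor does 0.86 stand alone: 0.92 is also planned, contrast FFR has its own cut-off, and kappa is a recognised chance-corrected measure of agreement between two binary classifications. Even for IMR, a kappa can be read as concordance or discordance beyond chance.

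Most of this stands. A reader might infer that objectives 4 and 6 cannot show agreement with FFR at all; that goes too far, because kappa at Pd/Pa 0.92 and contrast FFR 0.83 does so for binary status. A reader might also take the different cut-offs (0.83 or 0.92 against 0.80) as proof of misclassification, but step 3 shows that separate cut-offs can remove the effect of an offset.

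What does not stand is the defence of correlation. The method is named for a purpose that it does not serve, and nothing else in section 12 supplies the missing information for continuous values. Descriptive aims do not remove the need for a statistic that describes the stated quantity.

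**Conclusion.** The point holds in a limited form. For continuous values, correlation is the wrong tool for agreement; this needs no assumption, and the figures in steps 1 and 2 only illustrate it. For binary values, kappa is valid at Pd/Pa 0.92 and contrast FFR 0.83, but it is uninformative about the type of error at 0.86. The span of 0.20 to 0.875 there rests on assumed prevalences of 30-50%, 10-25% test-positive and a PPV of exactly 100% in this population. For CFR, IMR and RRR the label should be association.

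Two stronger readings are tempting and unsupported:

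- That kappa at 0.86 must be low. The documents give no sensitivity, a PPV of 100% does not by itself imply many missed lesions, and the upper end of the span is high.
- That IMR must score below chance against FFR. This needs a resistance model that is not in the documents. Varying its assumed inputs gave kappa from -0.48 to +0.17, negative throughout only when stenosis and microvascular resistance were taken as independent.

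This should be corrected before the final analysis, because cut-off pairs and statistics left open can otherwise be chosen after the results are seen.

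**What to change.** In section 12.1.3, objectives 4 and 6, pair each index with FFR in the same lesion and use confidence intervals that allow for several lesions per subject (for example, by resampling subjects). Then:

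1. For contrast FFR, report the mean difference from FFR and the limits of agreement.
2. For Pd/Pa and contrast FFR, report sensitivity, specificity, PPV and NPV at each stated cut-off against FFR 0.80, and also against 0.75. Give kappa at cut-off pairs named in advance. Read Pd/Pa 0.86 against FFR 0.80 as a rule-in test, through PPV and sensitivity.
3. For CFR, IMR and RRR, report the correlation and the 2×2 table of concordant and discordant lesions, described as association. State which correlation coefficient is used.

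The cost is revised wording and some extra tables. Section 6.4 already collects Pd/Pa and FFR for all evaluated lesions, and contrast FFR, CFR and IMR where the site measures them, so the change adds no burden for subjects. The downside is that several figures replace a single kappa or r per index, and the lesion-level intervals need a stated method for clustering.

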12.1.4 Additional Analysis

Descriptive statistics will be used to summarize each component of MACE rate at 12 months, and FFR, Pd/Pa and other PressureWire-derived indices (CFR, IMR, contrast FFR, RRR) measurements during index procedure and secondary procedures.

12.1.5 Reporting

The following data will be summarized and reported after 500, 1000, 1500 subjects complete 12-month follow-up visit:

- Investigator sites and enrollment status
- Demographic and baseline characteristics
- Serious Adverse events
- 12-month MACE rate

When all enrolled subjects complete 12-month follow-up visit, all statistical analyses described in this section will be conducted and a final clinical report will be completed.

13.0 DOCUMENT RETENTION

The Principal Investigator will maintain all clinical study documents from prior to, during and (as specified) after the clinical study on file at the site for a minimum of 15 years after the termination of this study, or longer as per local laws, or when it is no longer needed to support a marketing application, whichever is later.

The PI must contact the Sponsor prior to destroying or archiving off-site any records or reports pertaining to this study to ensure that they no longer need to be retained on-site.

All original subject files must be stored for the longest possible time permitted by the regulations at the hospital, research institute, or practice in question. If archiving can no longer be maintained at the site, the investigator will notify the Sponsor.

All data and documents will be made available on request of the relevant authorities in case of an audit.

The Sponsor will archive and retain all essential clinical study documents from prior, during and (as specified) after the clinical study as per requirements.

Clinical Investigational Plan

14.0 AMENDMENTS TO CLINICAL INVESTIGATIONAL PLAN

Study related documents such as the CIP, CRFs, Informed Consent form and other subject information, and other clinical study documents will be amended as needed throughout the clinical study, and a justification statement will be included with each amended section of a document. Proposed amendments to the CIP will be agreed upon between the Sponsor and the coordinating investigator (if applicable).

The amendments to the CIP and the subject's Informed Consent will be notified to, or approved by, the IRB/EC and regulatory authorities, if required. The version number and date of amendments will be documented.

The amendment will identify the changes made, the reason for the changes and if it is mandatory or optional to implement the amendment.

Any amendment affecting the subject requires that the subject be informed of the changes and a new consent be signed and dated by the investigator at the subject's next follow up per IRB/EC requirements.

Changes to, or formal clarifications of, the CIP will be documented in writing and provided to the investigators. This information will be incorporated when an amendment occurs.

15.0 STUDY COMMITTEES

15.1 STEERING COMMITTEE

The Steering Committee (SC) may be used to advise the sponsor during a clinical study, such as in the development of the study CIP, during the conduct of the study, during data analysis and/or presentation/publication of the study results. Membership may include National PIs or site investigators for the study under review.

16.0 INVESTIGATION SUSPENSION OR TERMINATION

16.1 PREMATURE TERMINATION OF THE WHOLE CLINICAL STUDY OR OF THE CLINICAL STUDY IN ONE OR MORE INVESTIGATIONAL SITES

The Sponsor reserves the right to stop the study at any stage, with appropriate written notice to the investigator.

Possible reasons for early termination of the study by the Sponsor, either at local, national or international level, may include, but are not limited to:

- The device / therapy fails to perform as intended
- Occurrence of USADE which cannot be prevented in future cases
- Sponsor's decision
- Recommendation from Steering Committee and Sponsor
- Request from Regulatory bodies
- Request of Ethics Committee(s)
- Concern for subject safety and welfare
- Failure to secure subject Informed Consent prior to any investigational activity

Clinical Investigational Plan

- Failure to report unanticipated adverse device effects within 72 hours to St. Jude Medical and the EC
- Repeated non-compliance with this CIP or the Clinical Trial Agreement
- Inability to successfully implement this CIP
- Violation of the Declaration of Helsinki 2008 (refer to Appendix C)
- Violation of applicable national or local laws and regulations
- Falsification of data, or any other breach of ethics or scientific principles

The study will be terminated according to applicable regulations.

The investigator may also discontinue participation in the clinical study with appropriate written notice to the Sponsor.

Should either of these events occur, the investigator will return all documents to the sponsor; provide a written statement as to why the premature termination has taken place and notify the IRB/EC and/or the Competent Authority (if applicable). Follow-up for all enrolled subjects will be as per CIP requirements.

A Principal Investigator, IRB/EC or regulatory authority may suspend or prematurely terminate participation in a clinical study at the investigational sites for which they are responsible.

If suspicion of an unacceptable risk to subjects arises during the clinical study or when so instructed by the IRB/EC or regulatory authority, St. Jude Medical may suspend the clinical study as appropriate while the risk is assessed. St. Jude Medical will terminate the clinical study if an unacceptable risk is confirmed.

St. Jude Medical will consider terminating or suspending the participation of a particular investigational site or investigator in the clinical study if monitoring or auditing identifies serious or repeated deviations on the part of an investigator.

If suspension or premature termination occurs, the terminating party will justify its decision in writing and promptly inform the other parties with whom they are in direct communication. The Principal Investigator and St. Jude Medical will keep each other informed of any communication received from IRB/EC or regulatory authority.

If for any reason St. Jude Medical suspends or prematurely terminates the study at an individual investigational site, St. Jude Medical will inform the responsible regulatory authority, as appropriate, and ensure that the IRB/EC are notified, either by the Principal Investigator or by St. Jude Medical. If the suspension or premature termination was in the interest of safety, St. Jude Medical will inform all other Principal Investigators.

If suspension or premature termination occurs, St. Jude Medical will remain responsible for providing resources to fulfill the obligations from the CIP and existing agreements for following up the subjects enrolled in the clinical study, and the Principal Investigator or authorized designee will promptly inform the enrolled subjects at his/her investigational site, if appropriate.

Clinical Investigational Plan

16.2 RESUMING THE STUDY AFTER TEMPORARY SUSPENSION

When St. Jude Medical concludes an analysis of the reasons for the suspension, implements the necessary corrective actions, and decides to lift the temporary suspension, St. Jude Medical will inform the Principal Investigators, IRB/EC, or regulatory authority, where appropriate, of the rationale, providing them with the relevant data supporting this decision.

Concurrence will be obtained before the clinical study resumes from the IRB/EC or regulatory authority where appropriate.

If subjects have been informed of the suspension, the Principal Investigator or authorized designee will inform them of the reasons for resumption.

16.3 STUDY CONCLUSION

The study will be concluded when:

- All sites are closed AND
- The Final report generated by St. Jude Medical has been provided to sites or St. Jude Medical has provided formal documentation of study closure

17.0 PUBLICATION POLICY

The results of the clinical study will be submitted for publication. Details of future publication and presentations will be outlined in a separate publication policy.

APPENDIX A: ABBREVIATIONS

Abbreviation	Term
ADE	Adverse Device Effect
AE	Adverse Event
CABG	Coronary artery bypass graft
CIP	Clinical Investigational Plan
CFR	Coronary flow reserve
CRF	Case Report Form
eCRF	Electronic Case Report Form
FFR	Fractional Flow Reserve
IB	Investigational Brochure
IC	Informed Consent
IMR	Index of Microcirculatory Resistance
IFU	Instructions For Use
IRB	Institutional Review Board
NSTEMI	Non-ST-elevation myocardial infarction
PCI	Percutaneous coronary intervention
PI	Principal Investigator
RDC	Remote Data Capture
RPI	Report of Prior Investigation
RRR	Resistance reserve ratio
SADE	Severe Adverse Device Effect
SAE	Severe Adverse Event
SC	Steering Committee
SJM	St. Jude Medical
STEMI	ST-elevation myocardial infarction
USADE	Unanticipated Severe Adverse Device Effect

Clinical Investigational Plan

APPENDIX B: STUDY GUIDELINES

Universal Classification of Myocardial Infarction

Type 1: Spontaneous myocardial infarction

Spontaneous myocardial infarction related to atherosclerotic plaque rupture, ulceration, Assuring, erosion, or dissection with resulting intraluminal thrombus in one or more of the coronary arteries leading to decreased myocardial blood flow or distal platelet emboli with ensuing myocyte necrosis. The patient may have underlying severe CAD but on occasion non-obstructive or no CAD.

Type 2: Myocardial infarction secondary to an ischemic imbalance

In instances of myocardial injury with necrosis where a condition other than CAD contributes to an imbalance between myocardial oxygen supply and/or demand, e.g. coronary endothelial dysfunction, coronary artery spasm, coronary embolism, tachy-/brady-arrhythmias, anemia, respiratory failure, hypotension, and hypertension with or without LVH.

Type 3: Myocardial infarction resulting in death when biomarker values are unavailable

Cardiac death with symptoms suggestive of myocardial ischemia and presumed new ischemic ECG changes or new LBBB, but death occurring before blood samples could be obtained, before cardiac biomarker could rise, or in rare cases cardiac biomarkers were not collected.

Type 4a: Myocardial infarction related to percutaneous coronary intervention (PCI)

Myocardial infarction associated with PCI is arbitrarily defined by elevation of cTn values >5 x 99th percentile URL in patients with normal baseline values (<99th percentile URL) or a rise of cTn values >20% if the baseline values are elevated and are stable or falling. In addition, either (i) symptoms suggestive of myocardial ischemia, or (ii) new ischemic ECG changes or new LBBB, or (iii) angiographic loss of patency of a major coronary artery or a side branch or persistent slow- or no-flow or embolization, or (iv) imaging demonstration of new loss of viable myocardium or new regional wall motion abnormality are required.

Type 4b: Myocardial infarction related to stent thrombosis

Myocardial infarction associated with stent thrombosis is detected by coronary angiography or autopsy in the setting of myocardial ischemia and with a rise and/or fall of cardiac biomarkers values with at least one value above the 99th percentile URL.

Type 5: Myocardial infarction related to coronary artery bypass grafting (CABG)

Myocardial infarction associated with CABG is arbitrarily defined by elevation of cardiac biomarker values >10 x 99th percentile URL in patients with normal baseline cTn values (<99th percentile URL). In addition, either (i) new pathological Q waves or new LBBB, or (ii) angiographic documented new graft or new native coronary artery occlusion, or (iii) imaging evidence of new loss of viable myocardium or new regional wall motion abnormality.

Hyperemic agent recommended doses

Agent	Recommended dose (IV)	Recommended dose (IC)
Adenosine	140 µg/kg/min	100 µg for right coronary artery 200 µg for left coronary artery
Adenosine 5'-triphosphate (ATP)	150 ug/kg/min	N/A
Nicorandil	N/A	2 mg
Regadenoson	0.4 mg	N/A

Clinical Investigational Plan

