3.2 STUDY DESIGN AND SCOPE

This study is a prospective, multicenter, multinational, multicontinental open label observational study.

This study will determine the use and clinical outcome of FFR-guided PCI on patients presenting with either stable coronary artery disease or ACS both for culprit and non-culprit lesions as well as during index and secondary procedures.

The FFR threshold for decision making is anticipated to be 0.80 in line with contemporary guidelines. Since the study is observational, there are no mandated thresholds for any of the physiologic measurements.

The study will also collect data on the routine use of coronary physiologic measurements such as adenosine-induced hyperemia FFR, FFR by contrast-induced hyperemia, Pd/Pa, and other alternate indices measurements.

The total duration of the study is expected to be 4 years, which includes 3 years for enrollment with 12 months of subject follow-up.

The clinical study will be conducted in approximately 200 centers in North America, EMEA, and Asia Pacific.

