6.4 PROCEDURE

Refer to the Instructions For Use (IFU) for procedural steps.

Fractional Flow Reserve (FFR) is an index determining the functional severity of narrowing(s) in the coronary arteries. FFR specifically identifies which coronary narrowing(s) are responsible for significantly obstructing the flow of blood to the heart muscle. FFR is used in conjunction with cardiac catheterization by placing the pressure wire distal to the coronary lesion and measuring pressure inside the artery. The pressure wire is then retracted until pressure is measured in the entire coronary artery.

The following data points will be collected during the procedure for all evaluated lesions (index or secondary procedures):

- Measurements of Pd/Pa
- Measurements of FFR with Adenosine induced hyperemia (IC or IV)
- MACE assessment (required)
- Prospective treatment decisions; initial treatment plan documentation shall be prior to FFR.

Other indices may be collected, according to the investigator's clinical practice and availability of appropriate devices (index or secondary procedures), as follows;

- IMR measurements
- CFR measurements
- Measurements of FFR with Contrast induced hyperemia
- Measurements of any additional novel resting indices (RI)

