8.1.4 Serious Adverse Device Effect (SADE)

Adverse device effect that has resulted in any of the consequences characteristic of a serious adverse event or that might have led to any of these consequences if suitable action had not been taken or intervention had not been made or if circumstances had been less opportune.

8.2 PROCEDURE FOR ASSESSING, RECORDING, AND REPORTING ADVERSE EVENTS, DEVICE DEFICIENCIES/COMPLAINTS, ADVERSE DEVICE EFFECTS, SERIOUS ADVERSE EVENTS, AND SERIOUS ADVERSE DEVICE EFFECTS:

Safety surveillance within this study and the safety reporting both performed by the investigator, starts as soon as the subject is enrolled in this study. The safety surveillance and the safety reporting will continue until the last investigational visit has been performed, the subject is deceased, the subject/investigator concludes his participation into the study or the subject/investigator withdraws the subject from the study, except as otherwise specified in the CIP.

Events considered reportable to sponsor are:

- Major adverse cardiac events (MACE) defined as all cause death, documented non-fatal myocardial infarction, and unplanned hospitalization leading to urgent revascularization
 - Myocardial infarction is defined according to the Universal Classification of Myocardial Infarction¹¹ (Appendix B)
 - Unplanned hospitalization leading to urgent revascularization is defined as unexpected hospitalization due to persisting or increasing complaints of chest pain (with or without ST-T changes) AND a revascularization is performed within the same hospitalization.
- Adverse device effects

All above events will be reported to the Sponsor, as soon as possible, but no later than 72 hours of first learning of the event. These will be reported to the Sponsor on dedicated case report forms or through the EDC system. The Investigator will record all adverse events and device deficiencies on the appropriate case report forms

Additional information may be requested, when required, by the Sponsor in order to support the reporting of AEs to regulatory authorities.

The Sponsor will ensure that all events and device deficiencies are reported to the relevant authorities as per regulations.

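### MACE includes procedure-related MI, and the planned analyses for Objectives 2 and 3 cannot separate it from later events, so the effect on the FFR comparisons is of unknown net direction

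*Combined protocol and SAP*

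**What the plan says.** - **Outcome.** Section 8.2: "Major adverse cardiac events (MACE) defined as all cause death, documented non-fatal myocardial infarction, and unplanned hospitalization leading to urgent revascularization". The same section adds: "Myocardial infarction is defined according to the Universal Classification of Myocardial Infarction", with reference to Appendix B.
- **MI types.** Appendix B lists types 1 to 3, then "Type 4a: Myocardial infarction related to percutaneous coronary intervention (PCI", type 4b (stent thrombosis) and type 5 (CABG). Nothing excludes periprocedural MI or starts the count after the procedure.
- **Timing.** Section 6.4 lists "MACE assessment (required" among the data collected at the procedure, and Section 6.5 repeats the assessment at discharge and one year.
- **Link to treatment.** Section 3.2: "The FFR threshold for decision making is anticipated to be 0.80 in line with contemporary guidelines". It then says that "there are no mandated thresholds for any of the physiologic measurements". Section 12.1.3 uses 0.8 as its first FFR cutoff, with 0.75 as a second.
- **Analysis.** Section 12.1.3 plans Fisher exact tests of 12-month MACE by changed or unchanged decision (Objective 2) and by FFR and resting-index group (Objective 3). Objective 3 adds logistic regression on the continuous values. A lesion-level GEE model is optional for both objectives. No covariate for, or stratification by, revascularization is stated.
- **Components.** Section 12.1.4: "Descriptive statistics will be used to summarize each component of MACE rate at 12 months". It states no split by MI type, FFR group or decision group.

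**The concern.** A type 4a MI needs a PCI and a type 5 MI needs a CABG. If FFR helps decide who is revascularized, it also helps decide who can have these events. A comparison of MACE by FFR group then mixes two things: events brought by the treatment that FFR prompted, and the later course of the disease. A reader of the final report will take MACE by FFR as the prognostic meaning of FFR.

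Objective 2 has the same difficulty in a less predictable form. A change from deferral to PCI exposes a subject to procedural MI, and a change from PCI to deferral removes that exposure. The net difference between the changed and unchanged groups depends on the mix of changes and on how many unchanged subjects had PCI.

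Ascertainment adds uncertainty. Type 4a requires a troponin rise plus a further criterion, but the assessment schedule lists no biomarker sampling. Across about 200 centers, detection will depend on local testing. Consent may follow the procedure (Section 3.6.1) and safety surveillance starts at enrollment (Section 8.2), so capture of procedural events may also be uneven.

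**Working it through.** The plan states no event rate, effect size or power (Section 12.1.1), so it has no figure of its own to reproduce. The check traces the definitions and then sizes the effect under stated assumptions.

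**Step 1: can the planned output separate the events?** By Section 8.2 the MACE components are death, MI and urgent revascularization. Types 1 and 4a therefore share one line in the Section 12.1.4 summary. The Section 12.1.3 tests use the full composite without regard to treatment received. The optional GEE model deals with several lesions per subject, not with treatment. The answer is no.

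**Step 2: size for Objective 3, cutoff 0.80.** From the documents: about 2000 subjects. Assumed: 1000 in each FFR group, 4% other MACE in both groups, PCI share *s* in each group, type 4a rate *r* per PCI subject.

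Group risk = 0.04 + *s* × *r*.

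For PCI 70% versus 5% and *r* = 3%:
- low FFR: 0.04 + 0.70 × 0.03 = 0.0610
- high FFR: 0.04 + 0.05 × 0.03 = 0.0415
- risk ratio: 0.0610 / 0.0415 = 1.47

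| PCI, low vs high FFR | Type 4a rate | MACE, low vs high | Risk ratio | Fisher rejection (two-sided 5%) |
|---|---|---|---|---|
| 70% vs 5% | 1% | 4.70% vs 4.05% | 1.16 | 9% |
| 70% vs 5% | 3% | 6.10% vs 4.15% | 1.47 | 47% |
| 70% vs 5% | 5% | 7.50% vs 4.25% | 1.76 | 86% |
| 70% vs 30% | 1% | 4.70% vs 4.30% | 1.09 | 6% |
| 70% vs 30% | 3% | 6.10% vs 4.90% | 1.24 | 19% |
| 70% vs 30% | 5% | 7.50% vs 5.50% | 1.36 | 41% |
| equal | any | equal | 1.00 | about 4% |

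Rejection rates are by enumeration of the two binomial distributions. Simulation gave 9/46/86% and 6/17/42% for the two unequal patterns.

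**Step 3: other assumptions.** Take 35% of 2000 subjects with low FFR, PCI in 85% versus 10%, and 5% other MACE, with risk = 1 − (1 − 0.05)(1 − *s* × *r*). Type 4a rates of 1%, 3% and 5% give risk ratios of 1.14, 1.40 and 1.65, and rejection of 10%, 45% and 83%. At a 3% type 4a rate, changing other MACE to 3% gives 1.66 (63%) and to 8% gives 1.25 (33%). With 500 subjects, the ACS target, the risk ratio of 1.40 is flagged in about 13% of trials.

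**Step 4: direction.** Steps 2 and 3 fix equal other MACE in the two groups, which need not hold. Take PCI 70% versus 5% and *r* = 3%, and let PCI lower other MACE in the low-FFR group to *x*. The composites are equal when *x* + 0.0210 = 0.0415, so *x* = 0.0205. A ratio of 0.0205 / 0.04 = 0.51 in other events would then appear as a composite ratio of 1.00. The mixture can create a difference or hide one.

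**The case against.** The best case for the plan is that this is an observational study whose objectives are to characterize outcomes and test association. Its scope is the use and clinical outcome of FFR-guided PCI, and a procedural MI is a real outcome of that pathway. Counting it in MACE is legitimate. This stands, and the main MACE definition need not change.

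Three further points stand in part:

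- **The threshold is not mandated.** Subjects with FFR above 0.80 may have PCI, for example of an ACS culprit lesion when another lesion was measured. A reader might infer that procedural MI falls in the low-FFR group by construction. The documents support only that it is likely to be more frequent there. The 70% versus 30% rows show the dilution.
- **Few type 4a events may be recorded.** Only documented MI counts, type 4a needs more than a troponin rise, and no sampling is scheduled. This favors the low end of the table, where rejection is 6–9% against about 4% with no difference. It also makes the count depend on the site.
- **Objective 5 is different.** A reader might extend the point to CFR, IMR, contrast FFR and RRR. No text makes these a treatment trigger, and Section 6.4 leaves their collection to local practice, so the documents do not support that extension.

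The component summary is not an answer, because it stops at MI as a whole.

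**Conclusion.** The point holds for Objectives 2 and 3 as a matter of interpretation. It is not a contradiction in the plan. As planned, the report could not tell a reader how much of any MACE difference by FFR group or decision group comes from procedural MI and how much from later events.

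At a 3% type 4a rate, the calculation with 4% other MACE and 1000 subjects per group spans a risk ratio from 1.00 (equal PCI use) through 1.24 (70% versus 30%) to 1.47 (70% versus 5%). PCI shares, type 4a rates and other MACE rates are all assumptions.

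A reader might infer that a significant association of low FFR with MACE would be procedural MI alone, or that the bias always makes low FFR look harmful. The documents support neither. They give no rates, and the background section cites benefits of PCI, including fewer infarctions in unstable angina and acute MI, which could offset or reverse the difference. For Objective 2 the direction depends on the mix of changes, which is unknown in advance.

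**What to change.** - **Section 12.1.3:** keep the main MACE analysis. For Objectives 2 and 3, add a co-reported analysis of MACE excluding periprocedural MI (types 4a and 5). State that type 4b also depends on a prior stent but is kept as a later event, and show it on its own line.
- **Section 12.1.4:** report MI by universal type, by FFR group and by changed/unchanged group.
- **Data capture:** confirm that the case report form records MI type. The forms are under separate cover (Appendix G), so this cannot be checked here. If they do not, take the type from the event source documents that are already reviewed remotely (Section 10.0).
- **Report:** say that the added analysis separates procedural from later events but does not remove confounding by treatment received.

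The cost is a few tables, possibly some classification of MI from source documents, and fewer events (so less precision) in the added analysis. The main endpoint and clinical management do not change.
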